13. REGULATORY CONSIDERATIONS

13.1 Protocol Review and Amendments

This protocol, the proposed informed consent and all forms of participant information related to the study (e.g., advertisements used to recruit participants) and any other necessary documents must be submitted, reviewed, and approved by a properly constituted IRB governing each study location.

Any changes made to the protocol must be submitted as amendments and must be approved by the IRB prior to implementation. Any changes in study conduct must be reported to the IRB. The CHLA Study Chair (or Protocol Chair) will disseminate protocol amendment information to all participating investigators.

All decisions of the IRB concerning the conduct of the study must be made in writing.

13.2 Informed Consent

All participants must be provided a consent form describing this study and providing sufficient information for participants to make an informed decision about their participation in this study. The formal consent of a participant, using the IRB approved consent form, must be obtained before the participant is involved in any study-related procedure. The consent form must be signed and dated by the participant or the participant's legally authorized representative, and by the person obtaining the consent. The participant must be given a copy of the signed and dated consent document. The original signed copy of the consent document must be retained in the medical record or research file.

13.3 Ethics

This study is to be conducted according to the following considerations, which represent good and sound research practice:

- State laws
- CHLA research policies and procedures
- It is understood that deviations from the protocol should be avoided, except when necessary to eliminate an immediate hazard to a research participant. In such case, the deviation must be reported to the IRB according to the local reporting policy.

13.4 Study Documentation

The investigator must prepare and maintain adequate and accurate case histories designed to record all observations and other data pertinent to the study for each research participant. This information enables the study to be fully documented and the study data to be subsequently verified.

Original source documents supporting entries in the case report forms include but are not limited to hospital records, clinical charts, laboratory and pharmacy records, recorded data from automated instruments, microfiches, photographic negatives, microfilm or magnetic media, and/or x-rays.

13.5 Records Retention

All study-related documents must be retained for the maximum period required by applicable federal regulations and guidelines or institutional policies. Study-related documents will be stored in a secured location accessible only to the investigators and formally designated study personnel.

13.6 Multi-Center Guidelines

This protocol will adhere to the policies and requirements of Children's Hospital Los Angeles (CHLA).

The CHLA Study Chair/Coordinating Center is responsible for distributing all IND Action Letters or Safety Reports to all participating institutions for submission to their individual IRBs.

Mechanisms will be in place to ensure quality assurance, protocol compliance, and adverse event reporting at each site.

Except in very unusual circumstances, each participating institution will order the agent(s) directly from the supplier. A participating site may order the agent(s) only after the initial IRB approval for the site has been forwarded to the Coordinating Center.

14. STATISTICAL CONSIDERATIONS

14.1 Primary Endpoints

The primary endpoint for the Phase I portion of the study is dose limiting toxicity during the first course of therapy, as defined in section 6.4.

The primary endpoint for the Phase II portion of the study is best overall response (BOR) during the first 12 cycles (nominally 48 weeks) of treatment. BOR will be assessed through the time of the post-12th cycle tumor assessment, or through the last tumor assessment time during this nominal period for patients in follow-up but who have withdrawn from protocol therapy, or through the last available tumor assessment for patients who are lost to follow-up during this time. The percent change in tumor sizes compared to baseline will be recorded at each evaluation time and will be used to define the categorical BOR as described below, per the definition of CR, PR, MR, SD, and PD in section 10.4.

- For tumors that regress compared to baseline during the assessment period without first satisfying the criteria for progressive disease (PD), BOR will be defined at the nadir of the tumor size compared to baseline provided that the percent reduction at the nadir satisfies the definition of CR, PR, or MR per section 10.4, with the BOR value of CR, PR, or MR determined by the percent reduction at this time. The associated time of BOR will also be recorded.
- For tumors that progress compared to baseline and satisfy the definition of PD without first satisfying the criterion at least for minor response (MR), BOR will be defined at the first time at which the percent increase in tumor size compared to baseline satisfies the criterion for PD. The BOR value will be PD. The associated time of BOR will also be recorded.
- For tumors that neither regress sufficient to satisfy the criterion for MR nor progress sufficiently to satisfy the criterion for PD during the assessment period, the BOR value will be SD. The time associated with BOR will be the last evaluation time during the 48 week evaluation period.

Patients will be considered evaluable for BOR if they have received at least one dose of treatment and have at least one post baseline tumor assessment.

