6.7 Duration of Follow-Up

Participants will be followed for AEs for 30 days after discontinuation of study therapy or until death, whichever occurs first. Participants who discontinue study therapy due to unacceptable adverse events will be followed until resolution or stabilization of the adverse event. For all patients that complete therapy or come off therapy for any other reason, toxicity assessment (for new SAEs and unresolved prior AEs) will continue for 30 days or until the events return to baseline. Patients

that start new therapy will not be evaluated for new SAEs. After the 30 days, survival data and MRI scans (if available) will be requested for all patients.

Recommended follow-up for patients that complete therapy will occur every 3 months (+/- 2 weeks) for the first year (can be more or less frequent) and then approximately annually until progression or change of therapy. Frequency of disease assessment in patients receiving continuation therapy is at the discretion of the investigator.

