14.4 Study Design for Phase II and Target Validation

For Strata 1 through 3, the Phase II study is viewed as three distinct Phase II studies, one corresponding to each of the three strata described in section 1. Each will be a single cohort study using best overall response (BOR – section 14.1) as the primary endpoint. While the primary analysis will be in the intent-to-treat (ITT) cohort – i.e., including all patients who are BOR evaluable per section 14.1, target accrual will be in terms of BOR -evaluable patients with **sufficient treatment (BORwST)**, defined as receiving at least 12 weeks of treatment or experiencing disease progression or death prior to 12 weeks. For the Target Validation Stratum 4, tumor resection prohibits evaluation of BOR as described above, so that analysis tumor response in this stratum will be descriptive.

Each of Stratum 1 and Stratum 2, target minimum accrual is 20 eligible BORwST patients, with up to 30 eligible patients allowed to ensure that at least 20 BORwST are accrued. Accrual to strata 1 and 2

will be halted once it is reasonably certain that this 20-patient target will be achieved. In the unlikely case that minimum of 20 BORwST patients is not reached, the study committee will consider whether an amendment to increase accrual is warranted. The accrual rate to Stratum 1 and Stratum 2 is estimated at approximately 1 per month.

For Stratum 3, target minimum accrual is also 20 eligible BORwST patients, with up to 30 eligible patients allowed. Accrual to this stratum will be halted once it is reasonably certain that the target of 20 BORwST patients will be achieved, or once both stratum 1 and stratum 2 have met accrual goals, whichever occurs first.

For Target Validation Stratum 4, accrual will be halted once it is reasonably certain that 20 patients are enrolled with pre- and post-treatment tumor specimens, or once both Stratum 1 and Stratum 2 have met accrual goals, whichever occurs first.

There will be no statistical monitoring rules for halting the study early either for lack of efficacy or futility.

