The primary analyses in Strata 1 and 2 will include all patients who are evaluable for BOR per section 14. The primary method of analysis will be an exact one-sided, one-sample test of the proportion of patients who achieve BOR of at least minor response (MR). With Type I error no greater than 10% at a response rate of 0.05, with a minimum of 20 patients there will be at least 85% power to detect a BOR CR/PR/MR rate of 25%. Hence, in each of Strata 1 and 2 there is sufficient power to discriminate between an unacceptable BOR rate of ≤ 0.05 and an achievable and clinical relevant BOR rate of ≥ 0.25 . Secondary analyses in these strata will include analysis of BOR in the BORwST cohort, as well as estimation of 12-month event-free survival (EFS) and recurrent/progression free survival (PFS) *via* the product limit estimator, and summarization of rates of toxicities in both the ITT and BORwST cohorts.

Analysis in Strata 3 and 4 (target validation) will be descriptive, in the former comprising estimation of the BOR rate, EFS, PFS, and in the latter comprising analysis of MED162 tumor concentration, ERK phosphorylation as an indicator of Ras/Raf/MEK/ERK pathway inhibition, and other related endpoints. Rates of toxicities will also be summaries for both strata.

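### The primary response window in 14.1 does not close when other anti-tumour therapy starts, so shrinkage on another treatment can count as a MEK162 response

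*Combined protocol and SAP*

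**What the plan says.** Section 14.1 sets the phase II primary endpoint as best overall response (BOR) in the first 12 cycles, nominally 48 weeks. For patients who stay on treatment, "BOR will be assessed through the time of the post-12th cycle tumor assessment". For those who stop early, the window runs "through the last tumor assessment time during this nominal period for patients in follow-up but who have withdrawn from protocol therapy". If the tumour shrinks without first meeting the criteria for progressive disease (PD), "BOR will be defined at the nadir of the tumor size compared to baseline", provided the reduction reaches at least minor response (MR). A patient is evaluable with one dose and one post-baseline assessment.

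Section 14.4 tests the proportion with MR or better in each of Strata 1 and 2 among all BOR-evaluable patients. The test is exact and one-sided, with type I error of at most 10% at a 5% rate and power of at least 85% at 25%. The accrual target is 20 patients with sufficient treatment (BORwST), "defined as receiving at least 12 weeks of treatment or experiencing disease progression or death prior to 12 weeks", with up to 30 eligible patients allowed. "Secondary analyses in these strata will include analysis of BOR in the BORwST cohort". For Stratum 4, 14.4 states that "tumor resection prohibits evaluation of BOR as described above".

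Section 6.7 says that after the 30-day safety period "survival data and MRI scans (if available) will be requested for all patients". It foresees a change of treatment, but says only that patients "that start new therapy will not be evaluated for new SAEs".

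**The concern.** Following patients after they stop MEK162 is a deliberate and reasonable choice, and it is not the problem. The problem is that the window stays open once something else is treating the tumour.

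Section 6.6 lets patients leave without progression, for example for toxicity, intercurrent illness, withdrawal or investigator judgement. Suppose a child stops for toxicity in cycle 5 without PD and starts another regimen, and a scan supplied at week 44 shows 25% shrinkage from baseline. Read as written, 14.1 records a MEK162 minor response. Section 10.4 asks for no confirmatory scan, so that one scan is enough.

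The stated objective is the preliminary efficacy of MEK162, tested against a fixed 5% rate with no control arm to offset responses earned by another treatment. For a given set of evaluable patients the error runs one way. Stable disease and PD both count as non-response, so later therapy can add a responder but cannot remove one.

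**Working it through.** **1. Is there a cut-off elsewhere?**

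- Sections 10.4 to 10.6 (response criteria, duration, central review) contain none, and neither does 14.4 for Strata 1 and 2.
- Section 6.5 prohibits anti-neoplastic therapy given concurrently with MEK162. It does not govern the period after MEK162 stops.
- Section 6.7 and the imaging footnotes to Tables 9-1 and 9-3 mention a change of therapy as an end point for follow-up visits. That is a recommended schedule for patients who complete therapy, whereas the 14.1 clause concerns patients who withdrew.
- The BORwST analysis is secondary. It drops patients who stop before 12 weeks without progression or death, but keeps a patient who switches later, such as the child above.

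**2. The plan's own figures.** The inputs from 14.4 are p0 = 0.05, p1 = 0.25, one-sided alpha ≤ 0.10 and n from 20 to 30. The critical value c is the smallest r with P(X ≥ r | n, 0.05) ≤ 0.10.

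| n | c | Type I error | Power at 25% |
|---|---|---|---|
| 20 | 3 | 7.5% | 90.9% |
| 22 | 3 | 9.5% | 93.9% |
| 23 | 4 | 2.6% | 86.3% |
| 30 | 4 | 6.1% | 96.3% |

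The rule is c = 3 for n = 20–22 and c = 4 for n = 23–30. The lowest power in the range is 86.3%, at n = 23. Both stated bounds hold.

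**3. Leverage of one response.** At n = 20, 2 responders give p = 0.264 and 3 give p = 0.075. At n = 23, 3 give p = 0.105 and 4 give p = 0.026. One misattributed response changes the verdict only when the genuine count is exactly one below c.

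**4. Type I error with contamination.** The documents supply no rates, so the following are assumptions. The true MEK162 response rate is 5%. In a stratum, k patients leave without PD and start other therapy. Each has chance q of a supplied scan showing at least 25% shrinkage by week 48. Then

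P(reject) = P(X + Y ≥ c), with X ~ Bin(n − k, 0.05) and Y ~ Bin(k, 0.05 + 0.95q).

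Worked case with n = 20, k = 2, q = 10%. Y has success probability 0.05 + 0.095 = 0.145, so P(Y = 0, 1, 2) = 0.7310, 0.2480, 0.0210. For X ~ Bin(18, 0.05), P(X ≥ 3, 2, 1) = 0.0581, 0.2265, 0.6028. The sum is 0.7310 × 0.0581 + 0.2480 × 0.2265 + 0.0210 × 0.6028 = 0.0425 + 0.0562 + 0.0127 ≈ 0.111.

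| k, q | n = 20 | n = 20 + k | n = 30 |
|---|---|---|---|
| 1, 10% | 9.2% | 10.3% | 7.2% |
| 2, 10% | 11.1% | 13.4% | 8.5% |
| 3, 20% | 19.9% | 8.2% | 14.4% |
| 4, 30% | 36.2% | 18.8% | 26.0% |

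The n = 20 column fits leavers who had at least 12 weeks of treatment and so count towards the 20. The n = 20 + k column fits leavers before 12 weeks, who are added to 20 BORwST patients. Values fall where n passes 22 because c rises from 3 to 4.

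**5. Break-even.** The value of q above which type I error exceeds 10%:

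| k | n = 20 | n = 20 + k | n = 30 |
|---|---|---|---|
| 1 | 14% | 8% | 34% |
| 2 | 7% | 1% | 16% |
| 3 | 5% | 25% | 10% |
| 4 | 3% | 17% | 8% |

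**6. Bias in the expected response rate at n = 20.** The bias is k × 0.95 × q / 20. For the four cases:

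- 1 × 0.95 × 0.10 / 20 = 0.475 percentage points
- 2 × 0.95 × 0.10 / 20 = 0.95 points
- 3 × 0.95 × 0.20 / 20 = 2.85 points
- 4 × 0.95 × 0.30 / 20 = 5.7 points

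**The case against.** The best defence is that the text is open, not wrong. The 14.1 clause covers only withdrawn patients who are still in follow-up, and an analyst could treat a child on another regimen as no longer in it. The glossary plans no further assessments after premature withdrawal unless the patient is followed for progression or survival. No passage schedules a scan like the week-44 one, and none says that the scans requested in 6.7 feed BOR. All responses are reviewed centrally at the end of the trial. Clinical progression counts as PD in phase II, which closes out more leavers. Section 4.2 excludes patients with acceptable established options, which may limit both k and q. In the two mildest scenarios type I error stays at or below 8.5% for every n from 23 to 30.

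These points bear on how often the problem arises, and they stand to that extent. They do not supply a rule. 14.1 sends withdrawn patients' scans into BOR up to week 48, and 6.7 asks for scans from everyone. Leaving the matter to end-of-trial review means deciding which scans count after the results are known. The Stratum 4 wording is only a loose parallel, since that surgery is planned after 7–21 days of drug. It does show the plan accepting that resection makes BOR uninterpretable.

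A further objection is that an early leaver's first post-baseline scan may come after the new therapy starts; without shrinkage, it adds a non-responder to the denominator. That is why upward-only bias is claimed here for a fixed evaluable set. A fix that keeps every 14.1-evaluable patient in the denominator deals with the case.

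**Conclusion.** The concern holds and should be fixed. As written, the primary endpoint can credit MEK162 with shrinkage produced by another treatment, and no other section prevents it. Exposure is limited to patients who leave without PD, start effective other therapy and have a scan within the nominal 48 weeks.

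The direction is upward for a given evaluable set. The size cannot be determined from the documents, because k and q are assumptions. In the scenarios shown, type I error ranges from 7.2% to 36.2%, so the stated 10% limit can be exceeded but need not be. The high figures require three or four such patients in a stratum with a 20–30% chance each. At n = 20, two patients at 10% already pass the limit.

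**What to change.** Add one sentence to 14.1: BOR is assessed through the earliest of the post-cycle-12 assessment, PD, or the last assessment before the first non-protocol anti-tumour therapy (drug, radiation, or surgery on a target lesion).

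- Keep off-drug scans taken before that therapy.
- Keep all BOR-evaluable patients in the denominator, and count those without CR, PR or MR by the cut-off as non-responders.
- Report the all-scans version as a sensitivity analysis.

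The cost is that sentence and the start date of the first non-protocol anti-tumour therapy on the follow-up form, which Table 12-1 names without listing its fields. No extra scans or patients are needed, and the sample size and decision rule do not change. The downside is that the observed response rate may be slightly lower.

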14.2 Secondary Endpoints

Secondary endpoints for Phase I include the grade and duration of CTCAE toxicities observed during treatment.

The concentration of MEK162 and its metabolite (AR00426032) in blood drawn at specified time-points (Table 8-1).

Secondary endpoints for Phase II include:

- Duration and grade of CTCAE toxicities observed during treatment

- Time to event, defined as the time from start of treatment to the first occurrence of tumor recurrence, tumor progression, occurrence of a second malignancy, or death from any cause. Patients event-free at last follow-up will be censored in analysis.
- Time to tumor recurrence/progression, defined as the time from start of treatment to the first occurrence of tumor recurrence, tumor progression, or death from disease. Patients without tumor recurrence at last follow-up, or who experience a second malignancy, or who die for causes unequivocally unrelated to tumor recurrence, will be censored in analysis.
- The concentration of investigational compound in tumor tissue after treatment with MEK162.
- Immunohistochemical assessment of PD effects on Ras/Raf/MEK/ERK pathway inhibition within tumor tissue (Strata 4 only) as measured by ERK phosphorylation before and after treatment with MEK162 for 7-14 days. Blood pharmacodynamic assessment will also be performed and correlated with tumor results.

14.3 Study Design for Phase I

Dose levels and starting dose are described in section 6.2. Patients will be enrolled according to a 3+3 dose escalation design. In brief, three patients will initially be enrolled and treated at starting dose level 1. If no DLTs are observed, dose will be escalated to dose level 2. If 1 DLT is observed, three additional patient will be enrolled to dose level 1. If at most 1 DLT is observed in six patients during course 1 of treatment then the dose will be escalated to dose level 2. If 2 or more DLTs are observed at a dose level, then the dose will be de-escalated. The MTD will be the maximum dose at which 6 patients have been treated and no more than 1 DLT has been observed. Refer to Appendix XV for a detailed description of the escalation rules.

To be considered DLT-evaluable, a patient must either have experienced an adverse event meeting DLT criteria during the first cycle of treatment, or have received at least 85% of doses in the first cycle. Only DLT-evaluable patients will be considered for dose escalation determinations.

14.4 Study Design for Phase II and Target Validation

For Strata 1 through 3, the Phase II study is viewed as three distinct Phase II studies, one corresponding to each of the three strata described in section 1. Each will be a single cohort study using best overall response (BOR – section 14.1) as the primary endpoint. While the primary analysis will be in the intent-to-treat (ITT) cohort – i.e., including all patients who are BOR evaluable per section 14.1, target accrual will be in terms of BOR -evaluable patients with **sufficient treatment (BORwST)**, defined as receiving at least 12 weeks of treatment or experiencing disease progression or death prior to 12 weeks. For the Target Validation Stratum 4, tumor resection prohibits evaluation of BOR as described above, so that analysis tumor response in this stratum will be descriptive.

Each of Stratum 1 and Stratum 2, target minimum accrual is 20 eligible BORwST patients, with up to 30 eligible patients allowed to ensure that at least 20 BORwST are accrued. Accrual to strata 1 and 2

will be halted once it is reasonably certain that this 20-patient target will be achieved. In the unlikely case that minimum of 20 BORwST patients is not reached, the study committee will consider whether an amendment to increase accrual is warranted. The accrual rate to Stratum 1 and Stratum 2 is estimated at approximately 1 per month.

For Stratum 3, target minimum accrual is also 20 eligible BORwST patients, with up to 30 eligible patients allowed. Accrual to this stratum will be halted once it is reasonably certain that the target of 20 BORwST patients will be achieved, or once both stratum 1 and stratum 2 have met accrual goals, whichever occurs first.

For Target Validation Stratum 4, accrual will be halted once it is reasonably certain that 20 patients are enrolled with pre- and post-treatment tumor specimens, or once both Stratum 1 and Stratum 2 have met accrual goals, whichever occurs first.

There will be no statistical monitoring rules for halting the study early either for lack of efficacy or futility.

The primary analyses in Strata 1 and 2 will include all patients who are evaluable for BOR per section 14. The primary method of analysis will be an exact one-sided, one-sample test of the proportion of patients who achieve BOR of at least minor response (MR). With Type I error no greater than 10% at a response rate of 0.05, with a minimum of 20 patients there will be at least 85% power to detect a BOR CR/PR/MR rate of 25%. Hence, in each of Strata 1 and 2 there is sufficient power to discriminate between an unacceptable BOR rate of ≤ 0.05 and an achievable and clinical relevant BOR rate of ≥ 0.25 . Secondary analyses in these strata will include analysis of BOR in the BORwST cohort, as well as estimation of 12-month event-free survival (EFS) and recurrent/progression free survival (PFS) *via* the product limit estimator, and summarization of rates of toxicities in both the ITT and BORwST cohorts.

Analysis in Strata 3 and 4 (target validation) will be descriptive, in the former comprising estimation of the BOR rate, EFS, PFS, and in the latter comprising analysis of MED162 tumor concentration, ERK phosphorylation as an indicator of Ras/Raf/MEK/ERK pathway inhibition, and other related endpoints. Rates of toxicities will also be summaries for both strata.

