¹² Laboratory tests will be collected and analyzed as per institutional standards. Examinations may be performed more frequently at the investigator's discretion if medically indicated; results should be recorded. At any time during the study, abnormal laboratory parameters which are clinically relevant (e.g., require dose modification and/or interruption of study drug, lead to clinical symptoms or signs, or require therapeutic intervention), whether specifically requested in the protocol or not, must be recorded.

¹³ Imaging to assess response will be obtained on day 1 of the following cycles (+/- 1 week for cycle 2, +/- 2 weeks thereafter): cycle 2, cycle 4, cycle 7, and cycle 10, and within 30 days following completion of study treatment. Cycle 2 imaging assessment is optional. Recommended follow-up for patients that complete therapy, including medical evaluation and MRI, will occur approximately every 3 months (can be more or less frequent) for the first year and then approximately yearly until progression or change of therapy.

¹⁴ For all visits, there is a \pm 3 days window on assessments to take into account scheduling over public or religious holidays if not explicitly specified otherwise. Laboratory assessments that were completed within 72 hours of Cycle 1, Day 1 (C1D1) do not need to be repeated.

¹⁵ For patients enrolled on the target validation stratum, all screening evaluations should be repeated prior to beginning post-operative cycle 1. If eligibility criteria (excluding surgical time windows) are not met, postoperative cycle 1 day 1 should be delayed up to 30 days until all eligibility criteria are met.

¹⁶ PedsQL brain tumor module will be administered at screening on day 1 of cycles 1, 2, 4, and 7 each subsequent cycle, and at the end of cycle 12 or at the off therapy visit (whichever occurs first). See section 8.4.

Table 9-4: Year 2 (Cycles 13-24) Required Observations

	Cycle 13	Cycle 16	Cycle 19	Cycle 22	End of Treatment See Table 9-3 or Table 9-1
Day 1 of cycle (+/- 2 weeks)	1	1	1	1	
Medical history / current medical conditions	X	X	X	X	
Height, weight	X	X	X	X	
Vital signs	X	X	X	X	
Physical examination	X	X	X	X	
Ophthalmologic examination (section 8.3)	X		X		
Pregnancy test (females of child-bearing potential only)	X	X	X	X	
Lansky/Karnofsky performance status (appendix X)	X	X	X	X	
ECHO	X	X	X	X	
CBC, differential, platelets	X	X	X	X	

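### Strata 1 and 2 toxicity rates are planned only in two efficacy-defined cohorts, so no named cohort counts every dosed child, and BORwST is selected on tolerating treatment

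*Combined protocol and SAP*

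**What the plan says.** Section 14.2 lists the grade and duration of CTCAE toxicities as a Phase II secondary endpoint and names no analysis population. Section 14.4 supplies the population for Strata 1 and 2: the secondary analyses will include "summarization of rates of toxicities in both the ITT and BORwST cohorts".

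The two cohorts are defined as follows.

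- **ITT.** Section 14.4 equates this with patients who are BOR-evaluable under section 14.1. A patient qualifies there "if they have received at least one dose of treatment and have at least one post baseline tumor assessment".
- **BORwST.** Section 14.4 says that "target accrual will be in terms of BOR -evaluable patients with" sufficient treatment, "defined as receiving at least 12 weeks of treatment or experiencing disease progression or death prior to 12 weeks". BORwST is therefore a subset of the ITT cohort.

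Accrual to each of Strata 1 and 2 aims at 20 BORwST patients, with "up to 30 eligible patients allowed to ensure that at least 20 BORwST are accrued". The same section foresees that 20 might not be reached and leaves the response to the study committee.

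Three provisions decide who has a post-baseline assessment. Table 9-3, footnote 13, schedules imaging on day 1 of cycles 2, 4, 7 and 10, and "within 30 days following completion of study treatment. Cycle 2 imaging assessment is optional". Section 14.1 counts assessments in the nominal 48-week period "for patients in follow-up but who have withdrawn from protocol therapy". Section 6.7 adds that, after 30 days off therapy, "survival data and MRI scans (if available) will be requested for all patients".

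For Strata 3 and 4, section 14.4 promises toxicity rates without naming a cohort.

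**The concern.** A toxicity rate should have everyone who was exposed in its denominator. Here membership depends on something else: a tumor assessment for the ITT cohort, and in addition 12 weeks of treatment (or earlier progression or death) for BORwST.

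The second condition is the more troublesome, because it depends on the outcome being summarised. Table 6-2 requires permanent discontinuation for some toxicities, for example retinal vein occlusion of any grade and Grade 4 rash. A child who stops for such an event at week 6, with no progression or death by week 12, leaves the BORwST denominator because of the event that the table is meant to count.

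The first condition matters less, but the label ITT invites a reader to assume that every treated child is included, and the definition does not ensure that.

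At stake is the descriptive safety profile by stratum. Section 3.3 reports only 6 DLT-evaluable Phase I children at the Phase II dose, so Phase II will supply most of this study's safety experience at that dose.

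**Working it through.** **The plan's own figure.** The documents give no figure for the toxicity cohorts. The design figure in section 14.4 is at least 85% power at a response rate of 0.25, with one-sided type I error of at most 10% at 0.05 and at least 20 patients. With the exact binomial and the smallest qualifying cut-off r at each n:

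- n = 20, r = 3: type I error 0.0755, power 0.909.
- n = 20 to 30: lowest power 0.863, at n = 23, r = 4 (type I error 0.0258).

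The claim reproduces. It concerns response in BOR-evaluable patients, and a change of toxicity population does not touch it.

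**Who is in which cohort.** This follows from the definitions in sections 14.1 and 14.4.

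| Dosed child | ITT | BORwST |
|---|---|---|
| 12 weeks of treatment, assessed | in | in |
| Progression or death before 12 weeks, assessed | in | in |
| Stops before 12 weeks for toxicity or another reason, no progression or death by then, assessed | in | out |
| No post-baseline tumor assessment recorded, including a child who dies first | out | out |

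**When a dosed child can lack an assessment.** The cycle 2 scan is optional, so the first required on-treatment scan is at cycle 4 day 1, that is after 3 × 28 = 84 days, with a window of 2 weeks either way. A child who stops before about week 10 enters the ITT cohort only through the optional scan, the end-of-treatment scan or a later assessment.

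**(a) ITT against all treated.** Let n be the number dosed in a stratum, with one child omitted. Let x be the number of ITT children with the toxicity, p = x/(n − 1), and t = 1 if the omitted child had it, otherwise 0.

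- All-treated rate − ITT rate = (x + t)/n − p = (t − p)/n, so the absolute shift is at most 1/n.
- n = 21 (20 in ITT plus 1 omitted): 1/21 = 4.8 points.
- n = 30 (the cap, all dosed): 1/30 = 3.3 points.
- For m omitted children the bound is m/n. It is zero if every dosed child has one assessment.

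**(b) BORwST against all treated.** If the target is just met at the cap, 30 − 20 = 10 children are outside BORwST, and 10/30 = 33%.

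The next lines use assumed numbers, to show how the three rates can differ. Suppose 4 of 20 BORwST children have a given toxicity (20.0%).

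- All 10 others had it: the all-treated rate is 14/30 = 46.7%. The ITT rate is 14/30 = 46.7% if all 10 were assessed, 12/28 = 42.9% if 2 were not, and 9/25 = 36.0% if 5 were not.
- None of the 10 had it: the all-treated rate is 4/30 = 13.3%, so BORwST is then too high.
- A milder case has 24 dosed, 1 unassessed and 3 other early stoppers, all 4 with the toxicity: all treated 8/24 = 33.3%, ITT 7/23 = 30.4%, BORwST 4/20 = 20.0%.

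**The case against.** The best answer is that the same sentence already provides a nearly complete view. A child who stops early for toxicity stays in the ITT cohort with one post-baseline assessment at any time in the period, and the plan schedules an end-of-treatment scan, counts assessments after withdrawal and requests later MRIs. BORwST is then a second, openly defined summary beside it. This stands as a limit on size: the ITT rate should lie close to the all-treated rate. It does not make the denominator independent of imaging, and it does nothing for BORwST.

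Second, section 14.4 says the secondary analyses will include these summaries, so an all-treated table is not excluded. That is true, but such a table is not prespecified, and the toxicity denominator is better fixed before the data are seen.

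Third, other provisions protect safety. Table 14-1 counts patients treated, and SAEs are reportable whether or not there is a scan. This also stands, but section 14.6 covers first-course DLTs pooled over Strata 1 to 3, not grade and duration by stratum. It is also fair to note that section 2.2, unlike 14.2, does not list toxicity among the Phase II secondary endpoints.

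A reader might infer more than the documents support:

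- **That at most a third of a stratum can fall outside BORwST.** Section 14.4 foresees fewer than 20 BORwST patients, so 10 of 30 is no ceiling. Nor is it an expectation, since accrual stops once 20 is reasonably certain.
- **That any child who dies early is in neither cohort.** This holds only if no post-baseline tumor assessment is recorded. Section 10.4 allows progression on clinical symptoms in Phase II, and the plan does not say whether that counts as an assessment.
- **That the background data give the size.** Adult combination-study discontinuations, CK elevations and Phase I first-cycle DLTs do not measure stopping before 12 weeks in these children.

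**Conclusion.** The point holds on the definitions. Neither cohort named for Strata 1 and 2 toxicity is an all-treated set.

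For the ITT cohort the effect is probably small: at most 4.8 points per omitted child with 21 dosed and 3.3 with 30, in either direction, and nothing if every dosed child is assessed. These figures assume that at least 20 children are in the ITT cohort; with fewer, the shift per child could be larger.

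For BORwST the rate is conditioned on tolerating 12 weeks or progressing or dying earlier, so it is probably too low. The direction is not certain, because BORwST also drops children who leave early for unrelated reasons, and its members mostly have longer exposure in which to record events. Its actual size cannot be computed, since the documents give no early-stopping rate for this population.

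A reader might conclude that toxicity in early stoppers disappears from the trial's safety record, or that the efficacy result is compromised. The documents support neither. Adverse events are collected from the first dose, and the primary test, its power and the DLT monitoring are unaffected. The defect lies in the denominator of a planned secondary summary. It should be corrected because correction costs almost nothing.

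**What to change.** In section 14.4, state that the main population for toxicity grade and duration is all patients who received at least one dose of MEK162, reported by stratum. Keep the BORwST summary as supplementary, labelled as patients with 12 weeks of treatment or earlier progression or death.

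The cost is one sentence and one more analysis population. No new data are needed, because sections 7.1 and 11.3 already have adverse events recorded from the start of treatment. The reported rates may be less favourable than those in BORwST.
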